6.4 STUDY INTERVENTION COMPLIANCE

Participants will receive study intervention directly from the Investigator or designee at the site, under medical supervision. The date and time of each dose administered in the clinic will be recorded in the source documents. The dose of study intervention and study participant identification will be confirmed at the time of dosing by a member of the study site staff other than the person administering the study intervention.

For a regional or national emergency declared by a governmental agency that results in travel restrictions, confinement, or restricted site access, contingency measures are included in [Section 10.9](#): Contingency measures for a regional or national emergency that is declared by a governmental agency.

6.5 DOSE MODIFICATION

Not applicable.

6.6 CONTINUED ACCESS TO INTERVENTION AFTER THE END OF THE STUDY

Eligible participants who complete the treatment period will be offered the opportunity to participate in the LTS study with amltelimab. Participants subsequently enrolled in the LTS study will not participate in the follow-up period of this trial but will have a follow up period after the LTS study.

6.7 TREATMENT OF OVERDOSE

For this study, any administration of [REDACTED] will be considered an overdose. No antidote is available for amltelimab.

Amltelimab has a [REDACTED] If severe adverse reactions occur after an overdose of amltelimab, then plasmapheresis (or infusion of albumin) to reduce the drug exposure may be considered.

NIMP overdose: any dose in excess of the maximum dose recommended in the respective medication labeling.

In the event of an overdose (symptomatic or asymptomatic), the Investigator/treating physician should:

- Contact the Sponsor immediately.
- Evaluate the participant to determine, in consultation with the Sponsor, whether study intervention should be interrupted or whether the dose should be reduced.
- Closely monitor the participant for any AE/SAE and laboratory abnormalities.
- Obtain a serum sample for PK analysis within 7 days from the date of the last dose of IMP if requested by the Sponsor (determined on a case-by-case basis).
- Document appropriately in the eCRF and report the overdose as an AESI (if symptomatic) within 24 hours of learning of the event.

6.8 CONCOMITANT THERAPY

Any medication or vaccine (including over-the-counter or prescription medicines, recreational drugs, vitamins, and/or herbal supplements) or other specific categories of interest that the participant is receiving at the time of enrollment or receives during the study must be recorded along with:

- Reason for use
- Dates of administration including start and end dates
- Dosage information including dose and frequency

The Sponsor should be contacted if there are any questions regarding concomitant or prior therapy.

Participants must abstain from taking prescription or nonprescription drugs (including vitamins, recreational drugs, and dietary or herbal supplements) within 7 days (or 14 days if the drug is a potential enzyme inducer) or 5 half-lives (whichever is longer) before the start of study intervention until completion of the follow-up visit, unless, in the opinion of the Investigator and Sponsor, the medication will not interfere with the study.

Paracetamol/acetaminophen, at doses of ≤ 2 g/day, is permitted for use any time during the study.

6.8.1 ICS in combination with one or two other controllers

On a daily basis throughout the study, the participant will use an eDiary to record daily use of ICS in combination with one or two other controllers as used just prior to screening.

The recognized asthma controllers for the study will include the following 5 classes: ICS, LABA, LAMA, anti-leukotrienes and methylxanthines. Please refer to [Section 10.10.3](#) for a list of commonly used asthma controller medication.

6.8.1.1 Screening period

Prior to screening, participants must be on a stable background therapy for at least 3 months, composed of medium to high dose of ICS (≥ 500 µg of fluticasone propionate daily or comparable ICS dosage to a maximum of 2000 µg/day of fluticasone propionate or clinically comparable [1]) in combination with a second controller medication (eg, LABA, LTRA, LAMA, methylxanthines), with or without third asthma controller medication. The second and third controller both should be used for at least 3 months with a stable dose ≥ 1 month prior to Visit 1. Participants requiring a third controller for their asthma will be considered eligible for this study, and it should also be used for at least 3 months with a stable dose ≥ 1 month prior to Visit 1. For Japan, please see [Section 10.8](#) for details.

If on chronic OCS treatment for the maintenance treatment of asthma, up to a maximum of 15 mg prednisone or equivalent daily or 30 mg every other day, must be on stable dose for ≥ 1 month prior to Visit 1 (see [Section 10.10.2](#) for comparison of systemic glucocorticoid preparations).

6.8.1.2 Randomized treatment period

During this period, participants will continue to take their controller medication(s) used during the screening period and will use an eDiary to record daily use. The dose and regimen should not be changed, except for the OCS, for which the dose could be changed per Investigator medical judgement.

6.8.1.3 Follow-up period

Upon completing the randomized treatment period, participants will proceed to be treated with the controller medication regimen and dose used during the randomized treatment period, which could be adjusted based on the medical judgment of the Investigator of the participants' asthma control status.

6.8.2 Reliever medication

Please refer to [Table 15](#) for a list of commonly used asthma reliever medications in [Section 10.10.3](#). Participants may administer SABA MDI and DPI as reliever medication as

needed during the study. Nebulizer solutions may be used as an alternative delivery method. Alternatively, low-dose ICS/formoterol may be used as reliever medication, per GINA 2021 recommendation (2) and Investigator's discretion. Reliever medication use will be reported by participants in the eDiary.

If a nebulizer is used, the dose administered via nebulizer must be converted to puffs using the nebulizer-to-puff conversion factor (Table 5, Table 6) (32) and entered in the eDiary.

Table 5 - Conversion of salbutamol/albuterol nebulizer solution dose to number of puffs

Salbutamol/albuterol nebulizer solution - total daily dose (mg)	Number of puffs*
2.5	4
5.0	8
7.5	12
10	16

*Conversion factor: salbutamol/albuterol nebulizer solution (2.5 mg) corresponds to 4 puffs.

Example of salbutamol/albuterol nebulizer-to-puff conversion: Participant received 3 salbutamol/albuterol nebulizer treatments (2.5 mg/treatment) between 7 AM and 11 AM. Total daily=7.5 mg or 12 puffs.

Table 6 - Conversion of levosalbutamol/levalbuterol nebulizer solution dose to number of puffs

Levosaltbutamol/levalbuterol nebulizer solution - total daily dose (mg)	Number of puffs*
0.63	2
1.25/1.26	4
1.89	6
2.5/2.52	8
3.15	10
3.75/3.78	12
5/5.04	16

*Conversion factor: levosalbutamol/levalbuterol nebulizer solution (1.25 mg) corresponds to 4 puffs

Example of levosalbutamol/levalbuterol nebulizer-to-puff Conversion: Participant received 3 levosalbutamol/levalbuterol nebulizer treatments (1.25 mg/treatment) between 7 AM and 11 AM. Total daily=3.75 mg or 12 puffs.

6.8.3 Allowed concomitant medication

Medications that have not been listed as exclusion criteria are permitted for use during the trial. These include the following:

- Oral contraceptives

- Intranasal, ocular or topical corticosteroids
- Previously initiated immunotherapy will be allowed to continue during the study.
- Antihistamines
- Paracetamol/acetaminophen
- COVID-19 vaccination:
 - To allow for an optimal immune response as well as protection against COVID-19, it is strongly recommended that participants complete their COVID-19 vaccination schedule (per local requirements) a minimum of 14 days prior to Baseline. The safety profile and effectiveness of COVID-19 vaccines in people with compromised immune systems or therapies (such as amltelimab) that modify or that suppress their immune response is not yet established.
 - While vaccination with an approved COVID-19 vaccine (including booster dose) is widely recommended (33), a participant's decision to have a COVID-19 booster during the study should only be made after discussing with his/her physician and the Investigator to assess the benefits/risks of receiving a COVID-19 vaccination during this study. In this instance, if the vaccine is authorized, available, and recommended by the local regulatory health authority, it should be administered according to the label or local health authority recommendations. The vaccine should not be administered within less than 14 days immediately prior to or following the IMP administration. Details of the COVID-19 vaccine should be recorded in the eCRF.

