Decreased antibody response to neoantigens and/or new vaccinations	
Clinical observation
 
In phase I study in healthy volunteers, SAR445229 appeared to have a pharmacodynamic effect from doses of 0.45 mg/kg and above based on the attenuation of the neoantigen (anti-KLH IgG and anti-KLH IgM) response. Potential impact on new vaccine response should be considered.
 

 

 

	
Assure that all pending and necessary vaccination (especially live/attenuated as well as for COVID-19) occurs per local recommendations and well in advance of dosing.
 
 Exclusion of vaccination with a live (attenuated) immunization within 12 weeks prior to Baseline; completion of required administrations of COVID-19 vaccine within 14 days prior to Baseline. In cases where booster vaccinations are recommended per local regulations it is not recommended that participants receive their COVID-19 vaccinations/boosters within less than 14 days immediately prior to or following the IMP administration.

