 - Creatinine $\geq 150 \mu\text{mol/L}$.
- E 15. Severe concomitant illness that would in the Investigator's opinion inhibit the participant's participation in the study, including for example, but not limited to, hypertension, renal disease, neurological conditions, heart failure and pulmonary disease.
- E 16. History (within last 2 years prior to Baseline) of prescription drug or substance abuse, including alcohol, considered significant by the Investigator.
- E 17. Elective surgery planned to be scheduled for any time in the period up to 3 months following the last dose of IMP.

Prior/concomitant therapy

- E 18. Anti-IgE mAb therapy (eg, omalizumab [Xolair]) within 130 days prior to Visit 1 or any other biologic therapy (including anti-IL4/4R, IL-5/5R, or anti-TSLP mAb) or systemic immunosuppressant (eg, methotrexate) to treat inflammatory disease or autoimmune disease (eg, rheumatoid arthritis, inflammatory bowel disease, primary biliary cirrhosis, systemic lupus erythematosus, multiple sclerosis) and other diseases, within 2 months or 5 half-lives prior to Visit 1, whichever is longer, except stable dose OCS used for the maintenance treatment of asthma.

- E 19. Participants who have received bronchial thermoplasty within 2 years prior to Visit 1 or plan to begin therapy during the screening period or the randomized treatment period.
- E 20. Treatment with a live (attenuated) immunization within 12 weeks prior to Baseline; completion of required administration of COVID-19 vaccine within 14 days prior to Baseline.
- E 21. History of hypersensitivity or allergy to any of the excipients or IMP or other allergy that, in the opinion of the Investigator, contraindicates participation in the study. Known or suspected hypersensitivity to amltelimab or excipients used in the presentation of amltelimab or in preparation for administration.
- E 22. Any prior use of anti-OX40 or anti-OX40L mAb, including amltelimab.

Prior/concurrent clinical study experience

- E 23. Investigational therapy for the treatment of asthma or other conditions within 5 half-lives or the limit of PD effects or 3 months where the $t_{1/2}$ is unknown.
- E 24. Concurrent participation in any other clinical study, including noninterventional studies.

Diagnostic assessments

Not applicable.

Other exclusions

- E 25. Individuals accommodated in an institution because of regulatory or legal order; prisoners or participants who are legally institutionalized.

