6.8.4 Prohibited concomitant medication

The following concomitant treatments are not permitted during the screening or treatment phases:

- Systemic steroids for more than 7 consecutive days (except systemic steroids to treat asthma exacerbations and for maintenance treatment of asthma within allowed doses initiated before participation in the study)
- Systemic immunosuppressant within 2 months or 5 half-lives prior to Visit 1, whichever is longer (eg, methotrexate, any anti-TNF mAbs, B and/or T cell targeted immunosuppressive therapies)
- Intravenous Ig (IVIG) therapy
- Anti-IgE therapy (eg, omalizumab [Xolair]) within 130 days prior to Visit 1 or any other biologic therapy within 2 months or 5 half-lives prior to Visit 1, whichever is longer
- Live Attenuated Vaccines within 12 weeks prior to baseline (see [Section 10.10.4](#))
- Beta-adrenergic receptor blockers (except for a selective beta-1 adrenergic receptor blocker used with stable dose at least 1 month prior to Visit 1)
- Asthma relievers other than SABA and low-dose ICS/formoterol: their use is not recommended during the study period. In case of use in exceptional circumstances (eg, prescribed by a physician not participating in the study), their use will be documented in the participant's file and reported in the eCRF.

- Initiation of immunotherapy
- Other investigational drugs

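### Protocol Section 6.8.4 contradicts itself: its lead-in bars on-treatment use, but the live-vaccine, immunosuppressant and biologic entries carry windows that end at baseline or Visit 1

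*Protocol*

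**What the plan says.** Section 6.8.3 of the Protocol gives the default rule, "Medications that have not been listed as exclusion criteria are permitted for use during the trial", and counts COVID-19 vaccination among the allowed items.

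Section 6.8.4 opens with "The following concomitant treatments are not permitted during the screening or treatment phases". Three of the entries below it carry their own time window:

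- "Live Attenuated Vaccines within 12 weeks prior to baseline"
- "Systemic immunosuppressant within 2 months or 5 half-lives prior to Visit 1, whichever is longer"
- anti-IgE therapy in the 130 days before Visit 1, or "any other biologic therapy within 2 months or 5 half-lives prior to Visit 1, whichever is longer"

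These windows match the eligibility rules in Section 5.2. E 20 reads "Treatment with a live (attenuated) immunization within 12 weeks prior to Baseline", and E 18 has the same 130-day and 2-month or 5-half-life limits.

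The Table 1 mitigation in Section 2.3.1 repeats the vaccine limit, "Exclusion of vaccination with a live (attenuated) immunization within 12 weeks prior to Baseline". The same cell also asks that outstanding vaccinations, live ones in particular, be completed well before dosing starts.

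Section 7.1.1 requires permanent withdrawal from study treatment after use of a systemic medication prohibited under 6.8.4, and likewise after a rescue treatment prohibited under 6.8.5.

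**The concern.** A washout window belongs in an eligibility criterion. In a list of treatments prohibited on study, it leaves a site unsure which period is barred. An investigator asked at Week 30 about a live vaccine finds a lead-in that says no and an entry that names only the weeks before baseline.

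The matter bears on safety. Table 1 says that blocking OX40L may reduce control of infections. On vaccination it reports that "SAR445229 appeared to have a pharmacodynamic effect from doses of 0.45 mg/kg and above", judged by the response to a new antigen, and advises that the effect on new vaccines be considered. Table 16 in Section 10.10.4 lists live products that an adult may be offered, such as intranasal influenza, shingles and yellow fever vaccines.

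The second consequence is procedural. Section 7.1.1 withdrawal depends on what 6.8.4 prohibits. If the immunosuppressant entry ends at Visit 1, a site cannot tell whether a participant who starts methotrexate on study must stop study treatment for good.

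**Working it through.** The plan states no figure on this point, so the check sets the texts side by side.

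**1. Entries in 6.8.4.** There are nine: systemic steroids, systemic immunosuppressants, IVIG, anti-IgE or other biologics, live vaccines, beta-blockers, other relievers, start of immunotherapy, and other investigational drugs. Three have a window that closes before treatment. The beta-blocker entry also mentions a time before Visit 1, but only to define who is exempt, so it reads correctly. IVIG, immunotherapy and investigational drugs have no window and read correctly under the lead-in.

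**2. Lead-in against entry.** Visit 1 is the screening visit. Treatment starts at baseline (Visit 2) and lasts 60 weeks.

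| Treatment | 6.8.4 entry ends at | Part of screening and treatment that the entry covers | Matching criterion |
|---|---|---|---|
| Live vaccines | Baseline | Screening only | E 20 |
| Systemic immunosuppressants | Visit 1 | None | E 18 |
| Anti-IgE or other biologics | Visit 1 | None | E 18 |

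For the last two rows, the entry and the lead-in describe periods that do not overlap. Taken literally, those entries prohibit nothing in the phases that the list is about.

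**3. Other text that applies on study.**

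- *Section 6.8, abstention rule.* It covers prescription and non-prescription drugs until the follow-up visit is completed. It can be waived where Investigator and Sponsor agree that there is no interference. It does not name vaccines, although the recording rule in the same section does. It is also not the section to which 7.1.1 points.
- *Section 6.8.3.* COVID-19 boosters have an on-study rule: not within 14 days of a dose in either direction. Live vaccines have no counterpart.
- *Section 6.8.5, Section 7.1.1 and SAP Table 4.* Anti-IL4R, anti-IL5/5R, anti-IgE and anti-TSLP antibodies lead to discontinuation of study treatment.

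**4. What remains open.** Removing the four asthma classes leaves live vaccines, systemic immunosuppressants (the entry gives methotrexate and anti-TNF antibodies as examples) and biologics outside asthma.

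**5. Participants on active drug.** With 420 randomized 2:2:1:2, the active arms hold 420 × (2 + 2 + 1)/7 = 300.

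**The case against.** The strongest reply is that 6.8.4 already bans these treatments. It is titled as a list of prohibited concomitant medication, and its lead-in names the treatment phase. Reading the lead-in as the ban and the window as an added washout gives effect to both, whereas the literal reading empties the lead-in for three entries. The Table 1 advice to vaccinate well before dosing points the same way. Section 6.8.3 can also be read as withholding permission from anything that E 18 or E 20 names at all, whatever the window. This stands as evidence of intent.

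A reader might therefore go too far in the other direction and infer that the Protocol permits live vaccines on treatment, or contains no ban. The documents do not support that. They contain a ban in the lead-in and entries that fail to carry it.

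The reply does not remove the contradiction. The reading that reconciles the two parts has to supply words that the entries lack, and the Table 1 advice is silent on a request made mid-treatment. Whether E 20 lists live vaccines in general or only before baseline is open on the wording of 6.8.3.

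For biologics the objection largely succeeds, since the asthma classes are covered elsewhere. Parts of Table 1 are blacked out or removed in the public copy, and the Investigator's Brochure is not available. Either may hold clearer guidance, but 6.8.3 and 6.8.4 are readable and are the sections that sites would consult.

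**Conclusion.** Section 6.8.4 contradicts itself in three of nine entries, and no readable text gives an unambiguous on-treatment bar on live vaccines. For systemic immunosuppressants and non-asthma biologics, what is unclear is mainly whether use triggers 7.1.1 withdrawal. A ban was probably intended, so this is a fault in an operative safety rule and not evidence of an unsafe design.

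The effect is probably small. The documents give no basis for counting live vaccines or immunosuppressant starts on study, and the treatment-policy primary analysis would keep the data of anyone affected.

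Two stronger inferences should be avoided. Counting every day after baseline as unprotected assumes the literal reading, which is the one in dispute. Comparing trial doses with the 0.45 mg/kg in Table 1 does not measure the hazard either, because that figure concerns the antibody response to a new antigen and not infection from a live vaccine.

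The follow-up period is a separate matter. The 6.8.4 lead-in does not reach it, but the 6.8 abstention rule does, if vaccines count as medication. An extension there is a choice for the sponsor and not a correction that the text demands.

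**What to change.** Reword three entries in 6.8.4:

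- *Live attenuated vaccines: from 12 weeks prior to baseline and throughout screening and treatment.*
- *Systemic immunosuppressants: from 2 months or 5 half-lives prior to Visit 1 (whichever is longer) and throughout screening and treatment.*
- *Anti-IgE therapy from 130 days, or any other biologic from 2 months or 5 half-lives (whichever is longer), prior to Visit 1 and throughout screening and treatment (rescue use is handled under 6.8.5).*

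In 6.8.3, limit the default permission to medications *not listed as exclusion criteria and not prohibited in 6.8.4 or 6.8.5*. Leave the 6.8 abstention rule unchanged.

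If the sponsor chooses to extend the live-vaccine bar into follow-up, the end point should read *until the EOS visit or entry into the LTS study*, because participants who enter that study skip this trial's follow-up.

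The cost is one sentence, three entries, an IRB/IEC submission and a note to sites. No assessment or analysis changes. The downside is that a participant who needs a live vaccine on study must postpone it or discuss stopping study treatment.

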6.8.4 Prohibited concomitant medication

The following concomitant treatments are not permitted during the screening or treatment phases:

- Systemic steroids for more than 7 consecutive days (except systemic steroids to treat asthma exacerbations and for maintenance treatment of asthma within allowed doses initiated before participation in the study)
- Systemic immunosuppressant within 2 months or 5 half-lives prior to Visit 1, whichever is longer (eg, methotrexate, any anti-TNF mAbs, B and/or T cell targeted immunosuppressive therapies)
- Intravenous Ig (IVIG) therapy
- Anti-IgE therapy (eg, omalizumab [Xolair]) within 130 days prior to Visit 1 or any other biologic therapy within 2 months or 5 half-lives prior to Visit 1, whichever is longer
- Live Attenuated Vaccines within 12 weeks prior to baseline (see [Section 10.10.4](#))
- Beta-adrenergic receptor blockers (except for a selective beta-1 adrenergic receptor blocker used with stable dose at least 1 month prior to Visit 1)
- Asthma relievers other than SABA and low-dose ICS/formoterol: their use is not recommended during the study period. In case of use in exceptional circumstances (eg, prescribed by a physician not participating in the study), their use will be documented in the participant's file and reported in the eCRF.

- Initiation of immunotherapy
- Other investigational drugs

6.8.5 Prohibited rescue medication and procedures

Rescue medications and procedures could be used per Investigator's medical judgement. The following rescue medications and procedures constitute a treatment failure:

- Anti-IL4R mAb (eg, dupilumab [Dupixent®])
- Anti-IL5 or IL-5R mAb (eg, benralizumab [Fasenra], mepolizumab [Nucala], or reslizumab [Cinqair])
- Anti-IgE mAb (eg, omalizumab [Xolair])
- Anti-TSLP mAb (eg, Tezepelumab [Tezspire®])
- Bronchial thermoplasty
- Initiation of continuous oral corticosteroid treatment during the study beyond 14 days consecutively

The date and time of rescue medication administration as well as the name, route of administration, reason for starting and dosage regimen of the rescue medication must be recorded.

